#### 2.5.3.2.5 NECK DISABILITY (NECK DISABILITY INDEX / NDI)

Neck functional capacity will be assessed with the self-reported NDI. The NDI captures disability/inability to perform daily activities due to neck pain. It consists of ten items, eight of which relate to various activities (personal care, lifting, driving, work, sleep, concentration, reading, entertainment) and two to pain in terms of intensity parameters and headache. Each item corresponds to six answers from which the participant should choose only one, the one that best represents their current situation. The lowest score for each item is zero, which is assigned as no pain and no functional limitation and the maximum five, which refers to the worst pain and maximum limitation. It is therefore understandable that the total score ranges from zero to fifty (Trouli *et al.*, 2008), with values 0-4 (0%8%) corresponding to no disability, 5-14 (10%-28%) to mild disability, 15-24 (30%48%) to moderate disability, 25-34 (50%-68%) to severe disability and 35-50 (70%-100%) to total disability (Magee, 2018).

The scale was translated and validated in the Greek population by Trouli et al. (2008) and proved to be a reliable, valid, and useful tool for research and clinical environment of Greek primary health care. Very good test-retest reliability (ICC: 0.93) and high internal consistency (Cronbach alpha=0.85) was indicated. Relation between the change score in the NDI and Global Rating of Change (GROC) was found (Spearman correlation coefficient = 0.3, P = 0.02). The Standard Error of Measurement (SEM) and the Minimal Detectable Change (MDC) were calculated as 0.64 and 1.78 respectively (Trouli *et al.*, 2008).

# 2.5.3.2.6. ANXIETY AND DEPRESSION (HOSPITAL ANXIETY AND DEPRESSION SCALE / HADS)

Anxiety and depression will be recorded by the HADS scale. It is a selfreport scale of 14 items, which are classified on a four-point scale (Likert scale) numbered

0-3. It has two subscales; HADs\_anxiety and HADs\_depression, each of which contains seven items. The total score ranges from 0-21 for each subscale (Michopoulos *et al.*, 2008), where values of 0-7 correspond to normal depression/anxiety, 8-10 to borderline abnormal, and 11-21 to abnormal (Hospital Anxiety and Depression Scale 2020).

The Greek version of the HADS has been proven to has good test-retest reliability (ICC, HADS = 0.944, ICC, HADS\_depression = 0.84 Kal ICC, HADS\_anxiety = 0.90) and high concurrent validity between the HADS, the Beck Depression Inventory (BDI) and the State-Trait Anxiety Inventory (STAI) (BDI, HADS = 0.75, BDI, HADS\_depression = 0.72, STAI, HADS = 0.76, STAI, HADS\_anxiety = 0.774) (Michopoulos *et al.*, 2008).

### 2.5.3.2.7. KINESIOPHOBIA (TAMPA SCALE KINESIOPHOBIA / TSK)

Fear of movement will be captured with the TSK\_GR which is a 17-item questionnaire with a score of 17-68. In 2005, it was validated by Georgoudis et al. (2005b) to the Greek population after examining 70 patients with chronic low back pain. Four values are assigned to each of the 17 questions; 1=Strongly disagree, 2=Disagree to some extent, 3=Agree to some extent, 4=Strongly agree, and the total score is obtained after reversing questions 4, 8, 12 and 16. If the score is 37 or less then it is associated with a low fear of movement, while on the contrary, 37 or more with increased fear of movement. The Greek version was shown to have validity and reliability. The internal consistency attributed to Cronbach's coefficient was 0.74 (a=0.74), a value considered satisfactory and even appeared increased (a=0.83) when questions 4, 8, 12 and 16 were not included (Georgoudis *et al.*, 2005b).

# 2.5.3.2.8. FEAR AND AVOIDANCE OF PAIN (FEAR- AVOIDANCE BELIEFS QUESTIONNAIRE / FABQ)

To record the perception of fear and the effort to avoid pain in relation to physical and work activities, the Greek version of the FABQ questionnaire (FABQ\_GR) will be chosen, which was validated by Georgoudis et al (2005a). The FABQ is a self-referential questionnaire consisting of 16 questions, each of which is scored from zero to six. Therefore, the total score is 96 points. Higher scores correspond to strong perceptions of fearing and avoiding pain.

Consequently, it consists of two subscales; the FABQ\_physical composed of four questions and assessing the aforementioned parameters in relation to physical

activities and the FABQ\_work, of seven questions on the same perceptions at work, with scores ranging between 0-24 and 0-42 respectively. The remaining five questions aim to distract the patient. Both models, as demonstrated by a clinical study conducted in the Greek population -70 patients with chronic low back pain-, had satisfactory internal validity (FABQ\_work Cronbach's a=0.86, FABQ\_physical Cronbach's a=0.72) (Georgoudis *et al.*, 2005a).

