# 2.3. RESEARCH HYPOTHESISES

Two main research questions are formulated regarding the effectiveness of ATM versus a standard treatment regimen consisting of acupuncture and stretching, but also the effectiveness of ATM as monotherapy, which will be investigated through appropriate statistical controls. The formal basis of statistical tests is the null hypothesis under which there is no association between the exposure and the outcome (Killeen, 2005). Starting from the assumption of no relationship, statistical tests quantify the probability that the observed relationship was observed by chance, due to the random sampling distribution. When the null hypothesis cannot be rejected then the observed relationship is attributable to chance rather than a true effect of the exposure on the outcome (Banerjee *et al.*, 2009).

Thus, the null hypotheses to be tested are formulated as follows:

- Research question 1: Effectiveness of ATM (intervention group before the intervention vs. the same group after the intervention)
  - Null hypothesis H0A1: The application of ATM does not affect the pain sensitivity assessed by the Pain Pressure Threshold (PPT) measured

with the pressure algometer (Commander Algometer) in patients with chronic neck pain (main hypothesis).

- Null hypothesis H0A2: The application of ATM does not affect the cervical range of motion (ROM) recorded with the Moover threedimensional (3D) Inertial Motion sensor in patients with chronic neck pain (secondary hypothesis).
- Null hypothesis H0A3: The application of ATM does not affect the strength of deep neck flexor muscles as measured by the Chattanooga Stabilizer Pressure Biofeedback in patients with chronic pain in the cervical spine (secondary hypothesis).
- Null hypothesis H0A4: The application of ATM does not affect the respiratory function assessed by the portable spirometer (MIR Spirodoc) in patients with chronic neck pain (secondary hypothesis).
- Null hypothesis H0A5: The application of ATM does not affect the pain in the cervical spine in terms of its intensity and quality, i.e., its sensory, emotional and behavioral dimensions using the McGill Pain Questionnaire-short form (SFMPQ) in patients with chronic neck pain (secondary hypothesis).

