# 2.5.3.2.4. INTENSITY AND QUALITY OF PAIN (SHORT-FORM McGill PAIN QUESTIONNAIRE / SFMPQ)

Pain will also be assessed subjectively with the SFMPQ questionnaire which includes its intensity as well as its sensory and affective dimensions (Melzack 1987). It consists of 11 sensory and 4 affective descriptors of pain. The patient rates each description on a four-point Likert type intensity scale, where 0 – no pain, 1 – mild pain, 2 – moderate pain and 3 – severe pain. SFMPQ also includes a ten-point Visual Analogue Scale (VAS) and a six-point rating scale describing the present intensity of pain (PPI), where: 0=No pain, 1=Mild, 2 =Annoying, 3=Painful, 4=Horrible, 5=Unbearable. The total score amounts to 45 points -33 for the sensory subscale, 12 for the affective subscale, 10 for the VAS and 5 for the PPI- (Neurotoolkit 2020). Furthermore, the SFMPQ is comprehensible and can be completed by people of different educational levels (even primary school graduates). It is a tool for multidimensional assessment of pain in patients with chronic musculoskeletal problems (the research sample in the Greek population consisted of patients

experiencing chronic pain with spinal and osteoarthritic conditions) (Georgoudis *et al.*, 2000).

The short form of the questionnaire was translated and validated to the Greek population in 2000 by Georgoudis et al. (2000) (the GREEK-SMFPQ/the GR-SFMPQ). The internal reliability of the Greek version of the SFMPQ has been indicated (Cronbach's  $\alpha$  value = 0.71) (Georgoudis et al., 2000).

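### The FABQ total of 96 includes five items the plan calls distractors, the parts listed for the 45-point SFMPQ total sum to 60, and the plan does not name the scores to be analysed

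*Combined protocol and SAP*

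**What the plan says.** **FABQ (section 2.5.3.2.8).** The questionnaire is described as "consisting of 16 questions, each of which is scored from zero to six". The plan then states "Therefore, the total score is 96 points" and, directly after, "Higher scores correspond to strong perceptions of fearing and avoiding pain". The next paragraph defines two subscales: FABQ_physical with four questions (0–24) and FABQ_work, "of seven questions on the same perceptions at work" (0–42). Of the other items it says: "The remaining five questions aim to distract the patient". Cronbach's alpha is given for the two subscales (0.86 work, 0.72 physical) and not for a 96-point total.

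**SFMPQ (section 2.5.3.2.4).** There are 11 sensory and 4 affective descriptors, each rated 0–3, together with a ten-point VAS and a PPI running from 0 to 5. The scoring sentence reads "The total score amounts to 45 points -33 for the sensory subscale, 12 for the affective subscale, 10 for the VAS" and goes on to add 5 for the PPI within the same list.

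**Analysis (section 2.9).** Change over time in the scales is modelled with linear mixed models, tested two-sided at 0.05. No FABQ or SFMPQ score or subscale is named as the dependent variable. FABQ serves H0A9/H0B9 and SFMPQ serves H0A5/H0B5, all labelled secondary in section 2.3.

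**The concern.** Each section gives a total that its own description of the instrument does not support. For the FABQ, a total read as fear-avoidance includes items that the plan says serve another purpose. For the SFMPQ, the listed parts do not add to the stated total, so the role of the VAS and PPI is unclear.

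These sections are the only place where the scores are defined, and section 2.9 adds nothing. An analyst could therefore use FABQ as 0–96, as 0–66 or as two subscales. SFMPQ could be analysed as the 0–45 descriptor sum, as a sum that includes the intensity items, or component by component. Section 2.10 promises a finding for every hypothesis, and no multiplicity rule is stated. The choice of score would then be open after the data are seen, and a result could not be tied with confidence to fear-avoidance, pain quality or pain intensity.

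**Working it through.** **FABQ, from the counts in section 2.5.3.2.8**

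- Plan's figure: 16 items × 6 = 96. It is reproduced only when all 16 items count.
- FABQ_physical: 4 × 6 = 24. FABQ_work: 7 × 6 = 42. Both match the stated ranges.
- Items in the subscales: 4 + 7 = 11, with maximum 24 + 42 = 66.
- Remaining items: 16 − 11 = 5, with maximum 5 × 6 = 30. Share of the total: 30 / 96 = 31%.

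**SFMPQ, from section 2.5.3.2.4**

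- Sensory: 11 × 3 = 33. Affective: 4 × 3 = 12. Sum: 33 + 12 = 45, the plan's figure.
- All four listed parts: 33 + 12 + 10 + 5 = 60. Adding only the VAS gives 55, and adding only the PPI gives 50. So 45 holds only with both left out.

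**Comparison.** Other ranges in the plan agree with their own item counts: NDI 10 × 5 = 50, HADS subscale 7 × 3 = 21, TSK 17 × 1 = 17 to 17 × 4 = 68, PCS 13 × 4 = 52.

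**Effect of including the distractors.** Assume equal item variances, a common correlation r between items, and the same shift in each of the 11 scored items. In units of item variance, a sum of k items has variance k + k(k − 1)r. The documents give no r for the whole scale, so r = 0.3 is an assumption.

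- 11 scored items: 11 + 110 × 0.3 = 44.
- Plus five distractors that are uncorrelated with everything and do not respond: 44 + 5 = 49. Ratio of standardised effects, 96-point to 66-point: √(44/49) = 0.95, a loss of about 5%.
- Five distractors that correlate 0.3 like the rest but do not respond: 16 + 240 × 0.3 = 88. Ratio √(44/88) = 0.71, a loss of 29%.
- Five distractors that correlate 0.3 and respond like the rest: 16/√88 = 1.71 against 11/√44 = 1.66, a gain of about 3%.

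**Sensitivity to r, first case.** The subscale alphas imply mean within-subscale correlations of α / (k − (k − 1)α): 0.86 / (7 − 6 × 0.86) = 0.47 for work and 0.72 / (4 − 3 × 0.72) = 0.39 for physical. At r = 0.4 the scored variance is 11 + 110 × 0.4 = 55 and the ratio is √(55/60) = 0.96. At r = 0.47 it is √(62.7/67.7) = 0.96. At r = 0.2 it is √(33/38) = 0.93. The loss is 4% to 7% over this range.

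**The case against.** The other side has a good deal right.

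- **A reader might infer that 96 is an arithmetic error.** It is not: 16 × 6 = 96. The difficulty is what the total is said to mean.
- **A reader might infer that H0A9/H0B9 will be tested on the 96-point total.** The documents do not say so. The hypothesis refers to physical activity and work, which matches the subscales, and reliability is quoted only for those. What stands against the plan is that 96 is nevertheless given as the total, with a direction of interpretation attached, and nothing later sets it aside.
- **A reader might infer that the distractors measure nothing, or that they cost 29% of the effect.** The plan says that they distract, which is a weaker statement. The 29% needs items that correlate with fear-avoidance as strongly as the scored ones do and yet ignore treatment entirely. Under other assumptions the result runs from a 3% gain to a 5% loss.
- **A reader might infer that a 60-point SFMPQ score is planned.** No section proposes one. The same section introduces the VAS and PPI as additions, and section 2.5.3 separates intensity from the sensory and affective dimensions. The likelier slip is a badly built list around a correct 45.
- **A reader might want FABQ_work limited to employed participants.** That is a separate choice, and this inconsistency gives no reason for it.

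All items are collected in any case, so every score remains recoverable.

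**Conclusion.** The point holds as a contradiction in scoring definitions for two secondary instruments, left open by section 2.9. For the FABQ, the plan states a total that conflicts with its own account of the items, and 30 of 96 points (31%) are affected. For the SFMPQ, the stated 45 is right for the descriptors, and the list of parts is wrong by 15 points.

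The statistical loss is small: about 5% of the standardised effect if the 96-point total were used and the distractors were unrelated noise, with r = 0.3, equal item variances and equal response of the scored items. The stronger reason to act is interpretation, together with fixing the score before the data are seen. The primary pressure-pain outcome and the sample size are untouched.

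A related wording slip is editorial. H0A5 and H1A5 promise "its sensory, emotional and behavioral dimensions using the McGill Pain Questionnaire-short form (SFMPQ", whereas sections 2.5.3 and 2.5.3.2.4 describe only intensity, sensory and affective content.

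**What to change.** - **Section 2.5.3.2.8:** delete the 96-point total. Name FABQ_physical (0–24) and FABQ_work (0–42) as the scores for H0A9/H0B9, and state that the five remaining items are not scored.
- **Section 2.5.3.2.4:** define the SFMPQ total as sensory plus affective, 0–45. Report VAS (0–10) and PPI (0–5) as separate intensity scores.
- **Section 2.9:** list these scores as the dependent variables.
- **Section 2.3:** remove the behavioural dimension from H0A5/H1A5 (editorial).

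**Cost.** No new data are needed. Two costs should be stated openly. First, there is more than one test per secondary hypothesis: two for FABQ and three for SFMPQ. At 0.05 each, and if the tests were independent, the chance of at least one false positive would be 1 − 0.95² = 9.8% and 1 − 0.95³ = 14.3%. Positive correlation between the scores lowers both. The plan should say how a hypothesis is judged when its scores disagree. Second, the subscales are not chosen for power. Under the same r = 0.3 assumptions, the standardised effect is proportional to 4/√7.6 = 1.45 for FABQ_physical and 7/√19.6 = 1.58 for FABQ_work, against 11/√49 = 1.57 for the 96-point total with noise distractors. The gain is a score that means what the hypothesis says.

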#### 2.5.3.2.9. PAIN CATASTOPHIZING (PAIN CATASTOPHIZING SCALE / PCS)

Pain catastrophizing will be calculated with the Pain Catastrophizing Scale (PCS). It is a 13-item instrument derived from the definitions of catastrophizing analyzed in the literature and from items from the catastrophizing subscale of the Coping Strategies Questionnaire (CSQ). Participants will be asked to recall past painful experiences and rate each of 13 thoughts or feelings on a five-point scale, where zero (0) corresponds to not at all and four (4) to constantly/all the time. Furthermore, it has been shown to have adequate to excellent internal consistency and requires a reading level of about grade six, which corresponds to the level of a 6-6.5-year-old child. It consists of three aspects of catastrophizing: Rumination (R) consisting of four questions, Magnification (M) consisting of three questions and Helplessness (H) consisting of six questions. The total score is calculated from the sum of the individual 13 question scores and ranges from zero to 52 (Sullivan 2009). The scale has been validated to the Greek population by Chatzidimitriou et al. (2006). The total form of Greek PCS has satisfactory internal consistency  $\{(Cronbach's alpha = 0.91) and its subscales (R: a = 0.79, M: a = 0.75, H: a = 0.88)\}$ . Total PCS has also satisfactory test-retest reliability {(ICC = 0.82) and the subscales (ICC: R: 0.87, M: 0.73, H: 0.86)}. Its convergent and divergent validity have also been demonstrated as PCS has high correlation with the CSQ (r = 0.89) and moderate correlation with the affective subscale of the SFMPQ (r = 0.38, p < 0.01), the sensory subscale of the SFMPQ (r = 0.23, p < 0.01), the kinesiophobia (a = 0.51, p < 0.01), the anxiety subscale of the HADS (r = 0.49, p < 0.01) and the depression subscale of the HADS (r = 0.45, p < 0.01) (Chatzidimitriou *et al.*, 2006).

### 2.5.3.2.10. QUALITY OF LIFE (SF-12 HEALTH SURVEY / SF-12)

Quality of life will be assessed using the SF-12 questionnaire, which has been validated to the Greek population. The SF-12 is the short, alternative form of the SF-

36 and assesses with the use of two items the parameters physical functioning (PF), physical and emotional role (role physical/RP, role emotional/RE) and mental health (MH) (Kontodimopoulos *et al.*, 2007). The score is 56,577 and 60,757 for physical role and mental health respectively (OrthoToolKit 2020). The parameters bodily pain (BP), general health (GH), social functioning (SF) and vitality (VT) are controlled by one object each. It consists of two factors of conceptual structure; Physical Component Summary (PCS) -correlated with PF, RP, BP and GH- and Mental Component Summary (MCS) -correlated more with SF, RE and MH-. It is noted that the VT item has a slightly higher correlation with the PCS score. The SF-12 Health Survey has demonstrated its construct, convergent, divergent and concurrent validity in Greek general population (Kontodimopoulos *et al.*, 2007).

# 2.5.3.2.11. CHANGE OF HEALTH CONDITION (GLOBAL PERCEIVED EFFECT / GPE)

The Global Perceived Effect (GPE) scale will rate the perceived change of the subject's health condition. It asks the patient to rate how much their condition has worsened or improved relatively to another predetermined point in time (Evans *et al.*, 2014). It is a numerical scale which consists of only one question with 5 possible answers. This scale is often used in musculoskeletal conditions, especially when they are chronic, such as chronic neck pain (Meisingset *et al.*, 2018). Despite the ease of application of the GPE, it is a challenge for patients to accurately remember the state in which they were recently and not to confuse the current state with the corresponding past state (Kamper *et al.*, 2010).

# 2.6. COMPLIANCE RATE

In addition to the aforementioned, in the survey will also be recorded the compliance rate of the participants in the two interventions. This process will be carried out through a paper form that each participant will receive and complete at the end of the ten sessions. On this paper form the exercises to be performed at home will be written and next to them an Y (YES) or N (NO) will be marked depending on whether patients will have performed them or not.

Participants' compliance with the exercise program at home will be assessed in two ways. The first way will include objective criteria such as whether they did the exercises that they were given, the frequency with which they implemented them and the way in which they performed them (i.e. continuously or with breaks). The second way will involve the subjective view of each participant, who will self-assess the compliance that they will have demonstrated. The two assessing ways of compliance will be reduced to percentage scales (0%-100%), where higher scores will indicate higher compliance.

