According to the philosophy of FM, the treatment of chronic neck pain requires an approach from the perspective of other components besides the cervical spine. In this light, neck pain can originate from the neck but also from other causes, including inadequate breathing patterns, pelvic tilts, insufficient differentiation of eye or head movements, overuse of the upper extremity musculature. An inseparable relationship is detected between the neck and the temporomandibular joint, i.e. the incorrect position of the former affects the function of the latter and conversely the increased tension in the temporomandibular joint changes the muscle tone of the neck. This category also includes the limited movement of the lumbar spine as well as the injury of the end of the foot that disrupts the smooth functioning of the biokinetic chain (Plastaras *et al.*, 2011).

In the A ATM group (intervention group) the ATM technique will be applied in group sessions (6-8 patients) by a physiotherapist, specialized in the FM with at least five years of experience. The ATM protocol will be implemented in ten sessions, two per week, of 50 minutes each, for a period of 5 weeks.

On the remaining days, home exercises will be given to the patients in the form of printed illustrated instructions for their correct execution. These ATM exercises, will be a repetition of the ATM lesson that they will have been taught and, will be performed once a day, until the next session, where participants will learn and implement the next ATM lesson. The execution rate of the movements and the movement pattern will be individualized, as they dependent on each patient.

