## 2.11. DISCUSSION

In the discussion the results will be recapitulated, analyzed and related to the existing literature. Each studied parameter of each research question will be assessed separately and the correlation based on the results obtained from the existing literature, which will be listed in the general part, will be highlighted. If the hypothesis is verified, then it will be compatible with the findings of the studies so far. Otherwise, it is against them. Finally, the above will be interpreted and the reason will be justified.

The aim of each study is to minimize the limitations, in order to draw safer conclusions and then to generalize the results.

The sample will consist of a wide age and social spectrum, which provides more reliability to the study and increases the power of the FM, giving the possibility of its application without limitations. Furthermore, a wide variety of parameters will be evaluated in a large sample size, providing the possibility of deriving statistically significant results. The number of the participants is satisfactory and larger than that of the majority of studies analyzed in the literature review. Additionally, recording the compliance rate is an additional advantage and is not included in the most studies.

In the limitations is included the design of the study, which is a 'single-blind' method, eliminating systematic error for the observer. Another limitation is represented by the heterogeneity in the severity of the patients' symptoms, which could be specified in the inclusion criteria. Also, the plethora of exclusion criteria, that were set due to the acupuncture may constitutes an obstacle to the promotion of the results in the general population. Last but not least, short-term or long-term follow-up will not be conducted.

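### Home-exercise compliance is taken once, after the last session, on a Y/N form that cannot recover daily frequency, means different things in the two arms, and can show the arm to the blinded second assessor

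*Combined protocol and SAP*

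**What the plan says.** Section 2.6 describes one instrument, "a paper form that each participant will receive and complete at the end of the ten sessions". It lists the home exercises, and "next to them an Y (YES) or N (NO) will be marked depending on whether patients will have performed them or not". Compliance is then to be assessed in two ways. The first, labelled objective, covers whether the exercises were done, "the frequency with which they implemented them", and whether they were done with or without breaks. The other is a self-rating: "The second way will involve the subjective view of each participant, who will self-assess the compliance that they will have demonstrated". Both are to be "reduced to percentage scales (0%-100%), where higher scores will indicate higher compliance". No scoring rule or denominator is given.

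The home task differs by arm. In section 2.5.2.1, ATM patients repeat the latest lesson on non-session days; these exercises "will be performed once a day, until the next session", when a new lesson replaces the old one. In the Group B A-S section, the same set of stretches is done at home once a day. Both protocols run for five weeks with ten sessions.

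Section 2.5.1.2 says the assessors are unaware of allocation. It has the second assessor both administer the compliance form and record the primary and secondary outcomes after treatment.

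Section 2.11 counts compliance as a strength: "recording the compliance rate is an additional advantage and is not included in the most studies". Section 2.9 names no analysis that uses it.

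**The concern.** The plan wants the frequency of a daily task, but the only item format it describes is a single yes or no per exercise, filled in after the task is over. No diary, daily log or check at each session is mentioned. Any answer about frequency would therefore have to be recalled over five weeks.

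Because the home task is built differently in the two arms, the same Y carries different information in each. Both interventions rely on home practice, so a reader will want to set the two compliance rates side by side. As collected, they would not be on the same footing.

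The second issue is blinding. A sheet listing ATM lessons or neck stretches identifies the arm to anyone who reads it. The person assigned to administer it also takes the post-treatment pressure-pain readings.

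**Working it through.** The plan states no compliance figure to reproduce. The check asks how little practice is compatible with a form on which every exercise is marked Y.

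**Inputs**
- Duration: 5 weeks; 10 sessions, two per week (both intervention sections).
- ATM home practice: once a day on non-session days, current lesson only; ten lessons (section 2.5.2.1).
- A-S home practice: the same stretches once a day (Group B A-S section).
- Form: Y/N per exercise, completed once at the end (section 2.6).

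**Days available**
- Total: 5 × 7 = 35.
- Non-session days: 35 − 10 = 25.

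**A-S arm.** One performance of the set lets the patient mark every line Y.
- All 35 days prescribed: 1/35 = 2.9%.
- Only non-session days counted: 1/25 = 4.0%.

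**ATM arm.** An all-Y form needs each lesson to have been practised at least once.
- Ten lessons over all non-session days: 10/25 = 40%.
- If the form is filled in at session 10, lesson 10 has not yet been practised at home and only nine lessons count. With the two weekly sessions *s* days apart, home days before session 10 are 5(*s* − 1) + 4(6 − *s*) = *s* + 19. For *s* = 2 to 5 this is 21 to 24 days, so the floor is 9/24 = 37.5% to 9/21 = 42.9%.
- The plan does not fix the spacing. If sessions fell on adjacent days, some lessons would have no home day. Leaving those lessons out, the floor is 4/20 = 20% (*s* = 1) or 5/25 = 20% (*s* = 6).

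| Arm | True adherence compatible with all Y |
|---|---|
| A-S | about 3% to 100% |
| ATM, at least one day between sessions | about 40% to 100% |

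**Blinding.** This needs no arithmetic. Section 2.5.1.2 says the assessors do not know the allocation, and then gives the second assessor a form whose content, under section 2.6, is the list of home exercises. Those lists differ completely between arms.

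**The case against.** The strongest reply is that the Y/N items are only part of the measure. Section 2.6 promises frequency, manner of performance and a self-rating, and the form itself is not in the document, so it may carry a frequency question. A patient who stretched once and one who stretched daily could differ on that question and on the self-rating. This stands: a reader might infer that compliance as a whole cannot separate good from poor adherence, but that is shown only for the Y/N items. What remains is that any further item would still be a single recall over five weeks, with no stated rule for turning it into a percentage.

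Other inferences also go too far.
- *The near-zero floor applies to both arms.* It does not. ATM lessons rotate, so the ATM floor is about 40%, not 4%.
- *The rate will be inflated.* The documents give neither the size nor the direction of recall error. Inflation is a risk.
- *The trial's efficacy result is compromised.* Compliance is recorded alongside the listed outcomes, has no hypothesis in section 2.3, and enters no model in section 2.9.
- *The second assessor will be unblinded before measuring.* The plan does not state the order of form and measurements, or whether the assessor reads the answers. The route is open; its use is not established.

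There is also a fair objection to the remedy. Handing a diary to the treating therapist may encourage socially desirable answers, and daily ticking may itself change adherence, perhaps unequally between group ATM sessions and individual A-S sessions. Both points stand and are treated as costs below.

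**Conclusion.** The concern holds in a limited form. One end-of-treatment self-report does not justify the label objective. Its Y/N part cannot recover daily frequency, and its meaning differs by arm: an all-Y form is compatible with as little as about 3% of prescribed days in A-S and about 40% in ATM. A between-arm comparison of such scores would not be interpretable, and the claim in section 2.11 that compliance recording is an advantage is only weakly supported.

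The figures assume that the Y/N marks are read as the share of exercises done and, for ATM, that at least one day separates sessions. The A-S figure moves from 2.9% to 4.0% if session days are not counted. That the frequency answers rest on recall is inferred from the late issue of the form and the absence of any running record.

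The consequence is for the interpretation of adherence, not for the primary test. The blinding route matters more, because it reaches the person taking the primary outcome. Its effect cannot be sized from the document. Overall this is a worthwhile low-cost improvement, not a serious defect.

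**What to change.** - **Timing and format.** Issue the form at the first session as a dated daily tick sheet. In ATM it should show the current lesson; in A-S, the stretching set.
- **Scoring.** Define compliance as days done divided by days prescribed, and state the denominator for each arm. The plan should say whether session days count in A-S, since this decides between 35 and 25.
- **Labelling.** Keep the self-rating if wanted, report it separately, and drop the word objective for anything self-reported.
- **Handling.** Have the therapists, who already know the arm, give out and take back the sheets, for example in sealed envelopes to limit social-desirability bias. Amend section 2.5.1.2 so that the second assessor never sees them. This closes one unblinding route, not every possible one.

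A sheet started at session one would also keep the days recorded by patients who stop early. The plan expects 20% dropout and describes no way for those patients to receive an end-of-treatment form.

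The costs are a redesigned sheet (more work in ATM because the lesson changes), a small daily task for patients, and a possible effect of self-monitoring on adherence that cannot be assumed equal in the two arms. No extra visits are needed, since patients already attend twice a week.
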